4.5. Analysis Sets

The following analysis populations will be used for the analysis of data as described within each analysis set:

Full Analysis Set (FAS): All patients who are randomized and received any amount of Study Drug (ISIS 678354 or placebo). The FAS represents the practically-feasible intent-to-treat (ITT) population as delineated in ICH Guideline E9. This population will be used for the primary analysis of efficacy.

Per Protocol Set (PPS): Subset of the FAS who received at least 5 monthly doses of Study Drug within the first 6 months (172 days) of the Treatment Period, and who have no significant protocol violations that could compromise the interpretation of efficacy. Significant violations will be determined prior to unblinding for statistical analysis. This population will be used for supportive inferences concerning efficacy.

Safety Set: All patients who are randomized and receive any amount of Study Drug. This population will be used for all safety analyses.

PK Population: All patients who are randomized and receive at least 1 dose of ISIS 678354, and have at least 1 evaluable concentration result post-first dose. This population will be used for analysis of PK data.

Analysis populations will be listed and also summarized with counts and percentages by treatment group and overall.

4.6. Demographic and Other Baseline Characteristics

Demographic data include age, age category (< 18, 18 to 64, ≥ 65 years), gender, ethnicity, race, weight, and body mass index (BMI).

Baseline characteristics include genetic confirmation and baseline lipids profile (fasting TG, apoC-III, total cholesterol, LDL cholesterol, HDL cholesterol, apoB, apoB-48, chylomicron-TG, VLDL, non-HDL-C, and apoA-1).

The following summaries will be provided:

- A summary of the demographic data, and baseline characteristics will be provided using the FAS population (Section 4.5).
- A summary of the demographic data and baseline characteristics will be provided using the PPS population (Section 4.5).
- A summary of the demographic data and baseline characteristics will be provided using the Safety Set (Section 4.5).

A by-subject listing of the demographic data and the baseline characteristics will be provided for all randomized subjects.

ISIS 678354-CS3

4.7. Medical History

The general medical history will be summarized using the Safety Set (Section 4.5). Frequency table will be provided by treatment group and overall, system organ class (SOC) and preferred term (PT), where SOC and PT are coded by Medical Dictionary for Regulatory Activities (MedDRA). The final MedDRA version used will be designated in the clinical study report.

A by-subject listing of medical history, including the reported term, the coded term, the start date, and the end date will be provided for all randomized subjects.

A separate table will be created for the targeted medical history using the Safety Set, and will include diabetes mellitus history, cardiac-related history (acute MI, percutaneous coronary intervention (PCI), CABG, unstable angina, heart failure, Stroke (CVA)/TIA, and revascularization), and pancreatitis history.

4.8. **Prior and Concomitant Medication**

Prior medications include medications started prior to the first dose of study medication regardless whether continued while on treatment or not. Concomitant medications include medications that patients are exposed to on or after the first dose of study medication. Partial or missing medication start date or end date will be imputed by the following imputation rules:

Start date:

- If year, month and day are all missing then assign the date of first dose of Study Drug
- If month and day are missing and year is:
 - earlier than the year of the first dose of Study Drug then assign December 31
 - o otherwise, assign January 1
- If only day is missing and month-year is:
 - \circ earlier than the month-year of the first dose of Study Drug then assign the last day of the month
 - otherwise, assign the first day of the month

End date: imputation will be performed for the end date only if the day or month is missing (i.e., year is present):

- If month and day are missing, then assign December 31
- If only day is missing, then assign the last day of the month

If the imputed start date is later than the imputed end date, then set the imputed start date to the imputed end date.

Prior and concomitant medication will be summarized using the Safety Set (Section 4.5) separately. Frequency table will be provided by treatment group, anatomical therapeutic chemical (ATC) drug class and preferred term (PT), where ATC and PT are coded by World Health Organization-Drug Dictionary Enhanced (WHO-DDE). The final WHO-DDE version used will be designated in the clinical study report.

The number and percentage of patients in each of the following categories will also be summarized by treatment group using the Safety Set:

• Not taking stains at baseline

o Initiated statins after study drug administration

- Taking statins at baseline
 - Increased statin dose or switched to higher intensity after study drug administration.

A by-subject listing of prior and concomitant medications will be provided using the Safety Set.

4.9. Efficacy Evaluation

4.9.1. Analysis and Data Conventions

4.9.1.1. Hypothesis

The study hypothesis is that ISIS 678354 can significantly improve efficacy parameters and is well-tolerated for patients with FCS. The null hypothesis for the treatment comparison will be that there is no difference between ISIS 678354 and Placebo in the percent change in fasting TG from Baseline at the primary analysis time point. The alternative hypothesis will be that there is a difference.

Symbolically, this is expressed as follows:

H(0): μ (test) = μ (reference)

H(1): μ (test) $\neq \mu$ (reference)

4.9.1.2. Handling of Dropouts or Missing Data

If there is missing TG data at baseline and primary analysis time point, a two-stage multiple imputation approach will be utilized.

First, patients with a missing fasting TG at the baseline will have missing values multiply imputed based on the observed baseline assessments from other patients. The Markov Chain Monte Carlo (MCMC) method will be used to impute the missing values. The imputation model will include baseline fasting TG value and 2 stratification factors (history of pancreatitis and previous treatment with Volanesorsen) (Schafer 1997; 1999). The TG values will be natural log-transformed before the imputation process, then back transformed after imputation to create the imputed data set. The SAS procedure PROC MI will be used to create 100 imputed datasets.

The following pseudo SAS code and seed (2438291) will be used to perform the multiple imputation for missing TG at baseline:

```
proc mi data = TG seed = 2438291 nimpute = 100 out=TG2;
transform log(baseline);
Mcmc;
var PANCR Volan baseline;
```

run;

The imputed baseline values will be merged with the observed post-baseline data and used for the second stage of imputation.

In the second stage of imputation, patients with a missing fasting TG at the primary analysis time point will have missing values multiply imputed based on the known assessments from the retrieved dropouts (patients who discontinue treatment before Week 23 but still have TG assessments at Weeks 23, 25, or 27), if there are a sufficient number of retrieved dropouts. The imputation model will contain the following variables: baseline fasting TG value, fasting TG values at post-baseline visits and 2 stratification factors (history of pancreatitis and previous treatment with volanesorsen), and the multiple imputation will be stratified by treatment group.

If there is no sufficient number of retrieved dropouts, missing TG value at the primary analysis time point will be imputed using a "wash-out" multiple imputation approach (Jump to Reference, J2R). With the approach, patients treated with ISIS 678354 will have missing TG values after the last dosing date multiply imputed based on baseline fasting TG, the 2 stratification factors of their own treatment group, and the imputation model for the placebo group. Patients in the placebo group will have missing TG values at post-baseline visits and the 2 stratification factors from the placebo group.

The "wash-out" multiple imputation will be preformed in the following steps:

1. The Markov Chain Monte Carlo (MCMC) method will be used under the multivariate normality assumption to impute all missing values by treatment group. The variable list for imputations will include the baseline value, as well as all available post-baseline value, and stratification factors. To conform to the multivariate normality assumption, baseline, and post-baseline fasting lipid data will be natural log-transformed before the imputation process, and the variable values will be back transformed to create the imputed data set. The SAS procedure PROC MI will be used in the multiple imputation. The MCMC method will impute primary analysis time point data for each of the 100 datasets from the first imputation stage. EM algorithm will be used to derive a set of initial parameter estimates for MCMC method. A non-informative prior (Jeffreys' prior) will be used to derive the posterior distribution of the parameters. A total of 100 imputed datasets will be created from the above 2-stage multiple imputation process.

The following pseudo SAS code and seed (2438291) will be used to perform the multiple imputation for each treatment group:

```
proc mi data = TG2 seed = 2438291 nimpute = 1;
transform log(baseline) log(week5) log(week9) log(month3)
log(week21) log(month6) log(week29) log(week37) log(week45)
Log(month12);
mcmc;
var PANCR Volan baseline week5 week9 month3 week21 month6
week29 week37 week45 month12;
by _imputation_;
```

run;

If there is no missing data at baseline, then the baseline imputation will not be performed. The second stage of imputation will be performed to create 100 imputed datasets.

- 2. A general linear model will be fitted using the data in the placebo group for each imputed dataset
- 3. For patients in both ISIS 678354 dose groups, the imputed values after last dose date will be replaced with the values imputed using J2R method (calculated using the patients' own baseline fasting TG, the 2 stratification factors, and the model from step 2)
- 4. The variable values will be back transformed from nature log scale to the original scale in the final imputed datasets.

For each of the 100 imputed datasets, the endpoint will be compared between ISIS 678354 treatment groups and pooled placebo using an ANCOVA model for continuous endpoints or logistic regression for binary endpoints as described in the primary analysis for each endpoint. The estimates from the 100 fitted models will be combined to provide an overall estimate with corresponding confidence intervals and p-value (Little & Rubin 2002)

The following pseudo SAS code will be used to estimate corresponding confidence intervals and p-value:

```
proc mianalyze data=diff;
    modeleffects estimate;
    stderr stderr;
```

run;

For the continuous endpoints, the treatment difference and the corresponding 95% CI will be presented. For the analyses using logistic regression, the odds ratio and the corresponding 95% CI will be presented.

Missing values at Months 3 and 12 and other lipid parameters will be imputed in a similar way to the primary analysis time point.

Only observed lipid data will be displayed in the data listings.

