10.6.3. Efficacy Analysis

10.6.3.1. Analysis of Primary Endpoint

The primary analysis of the primary endpoint is to compare the percent change from Baseline to the primary analysis time point in fasting TG between each ISIS 678354 treatment group vs. pooled placebo using an ANCOVA model in the FAS. The ANCOVA model will include the effects of treatment (ISIS 678354 80 mg, ISIS 678354 50 mg, or Placebo), 2 randomization stratification factors (history of pancreatitis and previous treatment with volanesorsen), and log-transformed baseline TG. To account for potential heterogeneity in variance, the 95% CI of the treatment differences will be calculated using the robust variance estimator based on the Bell and McCaffrey method (Imbens and Kolesár 2016). If patients have intercurrent event(s) before Week 23, e.g., treatment discontinuation, use of additional medication, changes in background or concomitant treatments, the Treatment Policy strategy will be implemented, the patients' assessments post intercurrent events will continue to be collected and utilized in the primary analysis. Patients with a missing TG value after discontinuation will have TG value multiply imputed at Primary analysis time point based on the known assessments from the retrieved dropouts (i.e., patients who discontinue before Week 23 but still have TG assessments at

Week 23, 25 or 27), if there is a sufficient number of retrieved dropouts. The imputation model will include the following variables: TG values at baseline and post-baseline visits and the 2 randomization stratification factors. The multiple imputation will be stratified by treatment group. If there is not a sufficient number of retrieved dropouts, missing TG value at the primary time point will be imputed using a "wash-out" (Jump to Reference, J2R) multiple imputation approach. With the approach, patients treated with ISIS 678354 who discontinue study will have missing post-discontinuation TG values multiply imputed based on the fasting TG at Baseline, 2 randomization stratification factors, and the imputation model for the placebo group. Patients in the placebo group who discontinue the study will have missing post-discontinuation TG values at Baseline and post-baseline visits from the placebo group.

It is anticipated that the rate of missing data is low.

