4.9.2. Primary Efficacy Variable

The primary efficacy analysis will take place after the last patient has completed the Week 53/ET visit and the database has been locked, and will be based on the percent change from Baseline in fasting TG at primary analysis time point.

The primary endpoint is the percentage change in fasting TG from Baseline to the primary analysis time point. The primary analysis of the primary endpoint is to compare the percent change from Baseline to the primary analysis time point in fasting TG between each ISIS 678354 treatment group (ISIS 678354 80 mg, ISIS 678354 50 mg) vs. pooled placebo using an ANCOVA model in the FAS. The ANCOVA model will use precent change from Baseline to the primary analysis time point in fasting TG as dependent variable, the two randomization stratification factors, prior history of pancreatitis within 10 years prior to Screening (yes vs. no), previous treatment with Volanesorsen (yes vs. no) and treatment group (ISIS 678354 80 mg, ISIS 678354 50 mg) as the fixed effects and nature log-transformed baseline fasting TG as a covariate. To account for potential heterogeneity in variance, the 95% CIs will be calculated using the robust variance estimator based on the Bell and McCaffrey method (Imbens & Kolesár 2016).

If patients have intercurrent event(s) before Week 23, e.g., treatment discontinuation, use of additional medication, changes in background or concomitant treatments, the Treatment Policy strategy will be implemented, the patients' assessments post intercurrent events will continue to be collected. All assessments including those post the intercurrent events will be utilized in the analysis.

Patients with missing TG value at the baseline and/or primary analysis time point will have fasting TG value multiply imputed using the multiple imputation methods described in Section 4.9.1.2 in the SAP. The are provided in the table below:

Treatments	ISIS 678354 80 mg Pooled placebo
Participant Population	Patients with FCS as defined by protocol eligibility criteria
Variable	Percent change from Baseline to primary analysis time point (average of Weeks 23, 25 and 27) in fasting TG
Intercurrent events (ICEs) and strategies	Discontinuation of study treatment prior to Week 23 Treatment policy strategy Disallowed concomitant therapy/procedure prior to Week 23 Treatment policy strategy
Population-level summary	Difference in means between ISIS 678354 80 mg and pooled placebo in the FAS

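### If the retrieved-dropout branch runs, SAP 4.9.1.2 lacks the protocol's after-discontinuation condition, so Month 6 TG missing in a patient still dosing would be predicted from patients who stopped

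*Combined protocol and SAP*

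**What the plan says.** Protocol 10.6.3.1 defines who is imputed in this branch: "Patients with a missing TG value after discontinuation will have TG value multiply imputed at Primary analysis time point based on the known assessments" of the retrieved dropouts. It gives no separate rule for a patient who is still dosing and has no Month 6 value.

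SAP 4.9.1.2 states the same branch without the discontinuation condition: "patients with a missing fasting TG at the primary analysis time point will have missing values multiply imputed based on the known assessments from" so-called retrieved dropouts. These donors are "patients who discontinue treatment before Week 23 but still have TG assessments at Weeks 23, 25, or 27". The branch applies "if there are a sufficient number of retrieved dropouts", and no threshold is given. The model contains "baseline fasting TG value, fasting TG values at post-baseline visits and 2 stratification factors" and is fitted by treatment group. It has no term for being on or off treatment.

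SAP 4.9.2 sends the primary analysis back to that section without narrowing it: "Patients with missing TG value at the baseline and/or primary analysis time point will have fasting TG value multiply imputed" by the methods given there. Its estimand tables apply a treatment-policy strategy to discontinuation before Week 23.

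The J2R fallback in SAP 4.9.1.2 is drawn more carefully. Step 1 imputes all missing values within each arm. In step 3, for the active arms, "the imputed values after last dose date will be replaced with the values imputed using J2R method", so only post-dosing values become reference-based.

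SAP 4.13 states that the planned methodology is unchanged from the protocol.

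**The concern.** Under a treatment-policy estimand, a patient who keeps dosing should contribute an outcome under continued dosing. Read literally, the SAP's retrieved-dropout branch predicts that patient's Month 6 TG from a relationship estimated only in patients of the same arm who had stopped. If TG rises after stopping, the active-arm mean is pulled toward placebo.

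Two consequences follow:

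- The same on-treatment patient is handled in two ways, depending on whether enough other patients happen to be retrieved dropouts. The two branches could then disagree for a reason unrelated to dropout.
- The rule reaches beyond the primary endpoint. SAP 4.9.1.2 says that Month 3, Month 12 and the other lipids are imputed along similar lines. Month 12 rests on two visits, not three, and Month 12 TG at 80 mg is the first secondary test. Both primary dose comparisons must succeed before any secondary endpoint is tested (SAP 4.9.1.3).

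**Working it through.** **Step 1. Compare the rules for one patient: active arm, still dosing, with Weeks 23, 25 and 27 all missing.**

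| Rule | Is this patient's Month 6 imputed from patients who stopped? |
|---|---|
| Protocol 10.6.3.1, retrieved-dropout branch | No. The value is not missing after discontinuation, and no other rule is stated. |
| SAP 4.9.1.2, retrieved-dropout branch | Yes. The only entry condition is a missing Month 6 value. |
| SAP 4.9.1.2, J2R fallback | No. The gap precedes the last dose, so the own-arm value from step 1 stands. |
| SAP 4.9.2, Sensitivity Analysis 3, second approach | No. Reference-based values apply only after the last dosing date. |

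Only the SAP's retrieved-dropout branch lacks a condition.

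**Step 2. Reproduce the planning figure (SAP 4.12).** Inputs: SD 46, difference 60 points, 14 per group, two-sided alpha 0.05, stated power 90%.

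- Standard error = 46 × √(2/14) = 17.39; noncentrality = 60/17.39 = 3.45.
- Power of a two-sample t-test on 26 degrees of freedom = 91.3%, which agrees with the stated 90%.
- With about 60 enrolled, randomized 1:1 to cohort and then 2:1, there are about 20 per active dose and 20 on pooled placebo. Standard error = 46 × √(2/20) = 14.55; noncentrality = 60/14.55 = 4.12; power = 98.0%.

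**Step 3. Bound the dilution.** Let m be the number of on-treatment patients in one active arm with no Month 6 value, and k the share of the drug effect that persists in patients who stopped.

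Shift toward zero = (m/20) × 60 × (1 − k)

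The documents give neither m nor k, so both are assumptions. Setting k = 0 borrows the SAP's assumption of no change on placebo as the off-drug level; SAP 4.12 gives no off-drug figure. The formula also ignores the patient's own earlier TG, so each row is an upper bound for its k.

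| m | k | Shift (points) | Remaining difference | Power, 20 vs 20 |
|---|---|---|---|---|
| 0 | any | 0 | 60 | 98.0% |
| 1 | 0 | 60/20 = 3.0 | 57.0 | 96.8% |
| 1 | 0.5 | 1.5 | 58.5 | 97.5% |
| 2 | 0 | 6.0 | 54.0 | 95.1% |
| 2 | 0.5 | 3.0 | 57.0 | 96.8% |
| 3 | 0 | 9.0 | 51.0 | 92.7% |
| 3 | 0.5 | 4.5 | 55.5 | 96.1% |

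At k = 1 the shift is 0 for every m. The power column changes only the difference and holds the SD at 46.

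**The case against.** **The branch may never run.** It needs an undefined sufficient number of retrieved dropouts, within arms of about 20. Going by the variable list in the SAP's J2R code, a model up to Month 6 would hold eight variables: two strata, baseline, Weeks 5, 9 and 21, Month 3 and Month 6. Detailed steps and code are written only for J2R. This stands, and it makes the concern conditional.

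**Few patients could qualify.** Month 6 is missing only if all three visits are missing, and the SAP 4.2.4 windows run without a gap from Day 149 to Day 190, which is 42 days. Redraws and home visits are provided for, and Protocol 10.6.3.1 expects little missing data. SAP 4.2.4 also lets local results stand in for missing central ones, though Protocol 6.2.1 says that blinded assays such as the lipid panel should not be tested locally. This largely stands. Such gaps are still foreseeable, because SAP 4.2.1 itself anticipates missing visits or data related to COVID-19.

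**A reader might infer that on-treatment patients are simply assigned an off-drug value.** The documents do not support that. The patient's own post-baseline TG is in the model, and Protocol 2.3.4 reports Phase 1 effects lasting at least 4 weeks after the last dose, so some donors may still carry effect. The error is softened. It is not removed, because the link from earlier TG to Month 6 is still learned only from patients who stopped.

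**The error is conservative and other analyses would show it.** If TG rises after stopping, the shift is against olezarsen. The completer analysis drops these patients, and the tipping-point analysis varies the imputed values. Both are sensitivity analyses, so they would expose the problem without correcting the primary test.

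**It is probably a drafting slip.** The protocol's wording, SAP 4.13 and the J2R text all point that way. A reader might infer a deliberate change of method; nothing in the documents shows one. A slip in the rule for the primary analysis still needs correcting.

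**Conclusion.** The point holds in conditional form. As written, the SAP's retrieved-dropout branch covers every missing Month 6 TG, contrary to Protocol 10.6.3.1, and the SAP does not declare the difference. If the branch runs and a patient still dosing lacks all three visits, that patient's value is predicted from the wrong group, and the drug effect tends to be diluted.

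The size is small. The upper bound is 3.0 points per affected patient for that dose, assuming 20 per arm, a 60-point effect, complete washout to the placebo assumption and no help from the patient's own data. It is 1.5 points if half the effect persists, and 0 if there is no such patient or the J2R branch is used. Two affected patients at full washout would take power from 98.0% to 95.1%.

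A reader might conclude that the primary comparison is materially biased or badly underpowered. The documents do not support that: they give no count of such patients, expect little missing data, and offer a fallback without this flaw. The extension to Month 12 and the other lipids is likewise an inference, since the donor definition is tied to Week 23 and no equivalent is spelled out for other time points.

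This should be corrected because a prespecified primary rule ought to treat each kind of patient in one way and match the protocol it claims to follow.

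**What to change.** In SAP 4.9.1.2:

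- Restrict retrieved-dropout imputation to TG missing after discontinuation of study treatment, as Protocol 10.6.3.1 says.
- Impute TG missing while on treatment from on-treatment patients of the same arm, under missing at random. The protocol has no such rule for this branch, so it should be recorded in SAP 4.13 as an addition.
- State the same split for Month 12 and the other lipids, including which patients count as donors at each time point.
- Define the sufficient number of retrieved dropouts, so that the choice of branch is fixed before unblinding.

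The split itself costs about one SAP sentence and one on/off-treatment flag in the imputation program; the donor definitions, the threshold and the SAP 4.13 entry need a few words more. No additional data are needed.

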6.1.2. Treatment Period

The Treatment Period is defined as the time between the first and the last dose of Study Drug plus 1 dosing interval. Patients will receive Study Drug administered by SC injection once every 4 weeks for 49 weeks. Collection and measurement of vital signs, physical examination results, ECGs, laboratory parameters (Appendix B), ISIS 678354 plasma concentrations, anti-drug antibody (ADA) and biomarker samples, patient reported outcome assessments, AEs and concomitant medication/procedure information will be performed according to the Schedule of Procedures in Appendix A.

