- The Treatment Period is 53 weeks. Eligible patients will have assessments at specified intervals throughout the 53-week Treatment Period. During the Treatment Period, Study Drug is administered by SC injection once every 4 weeks (Week 1 through Week 49).

• The Post-Treatment Follow-up Period is 13 weeks with assessments. Alternatively, following the Week 53 visit, eligible patients may elect to enroll in an OLE study pending study approval of this proposed study by the IRB/IEC and the appropriate regulatory authority.

The End-of-Study is defined as last patient, last visit. For individual patients, End-of-Study is defined as completion of their last study visit.

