4.2.3. Primary Analysis Time Point, Months 3 and 12, and Treatment Period

The primary analysis time point is defined as the average of Weeks 23, 25, and 27. If 1 or 2 of the 3 assessments are missing, then non-missing assessments will be used. Month 3 is defined as the average of Weeks 13 and 17. Month 12 is defined as the average of Weeks 51 and 53. For Month 3 or Month 12, if 1 assessment is missing, then non-missing assessment will be used.

The treatment period is defined as the time period from the first dose administration to the earliest date from 42 days after the last dose of Study Drug and last contact date within the study.

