4.9.3. Secondary Efficacy Variables

In order to control the type I error, a sequential closed testing procedure will be employed with the sequence of endpoints defined as in Section 4.9.1.3 above. Testing of secondary endpoints will be performed only if the treatment comparison of the primary analysis of the primary endpoint is statistically significant (p < 0.05) for both ISIS 678354 80-mg and 50-mg treatment groups. Testing of the secondary endpoints will be conducted according to the following sequence: if the primary analysis of the first secondary endpoint (comparison of percent change in fasting TG from Baseline to Month 12 between ISIS 678354 80-mg treatment group and pooled placebo in FAS) is statistically significant (p < 0.05) then the second ary endpoint (comparison of percent change in fasting apoC-III from Baseline to the primary analysis time point between ISIS 678354 80-mg treatment group and pooled placebo in FAS) will be tested. However, if the treatment comparison based on the first secondary endpoint is not statistically significant, then all endpoints of lower rank will be considered exploratory. This process is repeated with each subsequent secondary endpoint.

4.9.3.1. Percentage Change from Baseline in Fasting TG at Month 12

The percent change in fasting TG from Baseline to Month 12 in the FAS will be analyzed in the same way as the primary analysis of the primary endpoint. The intercurrent events will be handled using the Treatment Policy strategy.

A 2-dimensional tipping-point analysis will be conducted in the FAS as a sensitivity analysis.

Descriptive statistics and cumulative distribution curves will be provided for observed fasting TG levels and percent change in TG in each treatment group at Month 12.

4.9.3.2. Proportion of Patients who Achieve ≥ 40% Reduction in Fasting TG from Baseline at the Primary Analysis Time Point

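### The SAP's jump-to-reference fallback has no discontinuation condition, so patients who completed dosing but lack Month 12 lipids are imputed as placebo

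*Combined protocol and SAP*

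**What the plan says.** SAP 4.9.1.2 has two routes for a missing post-baseline TG value. The preferred route borrows from retrieved dropouts. The fallback opens with "If there is no sufficient number of retrieved dropouts" and uses J2R. Under it, "patients treated with ISIS 678354 will have missing TG values after the last dosing date multiply imputed based on baseline fasting TG", together with the two stratification factors and the placebo group's imputation model. In the four-step algorithm, step 1 imputes every missing value within treatment group, and the code lists month12 among the variables. Step 3 then says that, for both dose groups, "the imputed values after last dose date will be replaced with the values imputed using J2R method". Neither sentence asks whether the patient discontinued.

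The same section extends the method: "Missing values at Months 3 and 12 and other lipid parameters will be imputed in a similar way to the primary analysis time point". SAP 4.9.3.1 adds: "The percent change in fasting TG from Baseline to Month 12 in the FAS will be analyzed in the same way as the primary analysis". Month 12 is the average of Weeks 51 and 53, and SAP 4.2.3 states: "For Month 3 or Month 12, if 1 assessment is missing, then non-missing assessment will be used". On dosing, SAP 3.1 states: "Study Drug is administered by SC injection once every 4 weeks (Week 1 through Week 49". Protocol 6.1.2 states: "The Treatment Period is defined as the time between the first and the last dose of Study Drug plus 1 dosing interval".

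Protocol 10.6.3.1 confines J2R to active-arm patients who discontinue the study, and to values missing after they do so. Protocol 10.6.3.2 carries the primary method over to Month 12 TG. SAP 4.13 reports no departure from the protocol's methods.

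**The concern.** J2R represents the loss of effect after a patient stops drug. At Month 6 the last dosing date is a workable proxy for stopping, because anyone still on treatment has later doses. At Month 12 the proxy fails, because every patient's last scheduled dose precedes both visits. The rule then treats a patient who finished treatment as if the drug had never been given.

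That is not what the treatment-policy strategy targets, since such a patient has no discontinuation to account for. It also sits badly with Protocol 2.3.4, which reports Phase 1 effects lasting at least four weeks after the last dose. Week 53 is exactly four weeks after dose 13.

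Eight of the 28 ranked secondary comparisons concern Month 12 lipids (endpoints 1, 3, 7, 9, 18, 19, 22 and 23), including the first in the sequence. Their estimates would be pulled toward no effect by patients who were still on treatment, through a departure from the protocol that the SAP does not declare.

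**Working it through.** **1. Dates** (dosing from Protocol 8.1; visit days from Protocol Appendix A)

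- Dose *i* falls on Day 1 + 28(*i* − 1). Dose 13: 1 + 28 × 12 = Day 337 (Week 49).
- Week 51 is Day 351, which is 351 − 337 = 14 days later. Week 53 is Day 365, which is 28 days later.
- With the ±3-day windows, the latest Week 49 dose (Day 340) still precedes the earliest Week 51 visit (Day 348).
- The protocol's Treatment Period for a completer ends at 337 + 28 = Day 365. The SAP 4.2.3 version can run to 337 + 42 = Day 379. Both scheduled visits lie inside either period.

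**2. One patient traced through the algorithm.** Take an active-arm patient with all 13 doses who remains in the study.

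| Missing | Step 1 | After the last dose? | Step 3 | Final value |
|---|---|---|---|---|
| Weeks 23, 25 and 27 | own arm | No; doses continue to Day 337 | not applied | own arm |
| Weeks 51 and 53 | own arm | Yes | overwritten | placebo prediction |

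Under Protocol 10.6.3.1 this patient has not discontinued, so J2R does not apply in either row.

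**3. The SAP's other wording.** In SAP 4.9.2, Sensitivity Analysis 3, item 1 requires treatment discontinuation (for adverse event or lack of efficacy) as well as a value after the last dosing date. Item 2 has no discontinuation condition, although the matching analysis in Protocol 10.6.3.1 does.

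**4. The plan's own power figure.** Inputs from Protocol 10.2: difference 60, SD 46, 14 per group, two-sided 0.05.

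- SE = 46 × √(2/14) = 17.4; noncentrality = 60/17.4 = 3.45; 26 df.
- Noncentral-t power = 91.3%, against the stated 90%. Reproduced.

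**5. Size at Month 12.** Sixty patients split 1:1 and then 2:1 give 20 per active arm and 20 pooled placebo. I carry the Month 6 planning SD and effect to Month 12 and add a 40-point scenario; both are assumptions. With none affected, SE = 46 × √(2/20) = 14.5, and power is 98.0% at 60 points and 76.4% at 40.

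If *k* active patients are imputed at the placebo mean, the expected difference is Δ × (1 − *k*/20). The power with *k* affected was simulated with 12,000 trials per cell and normal errors. Each trial used 50 J2R imputations from the posterior of the placebo mean and variance, unequal-variance standard errors and Rubin's rules with small-sample df.

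| True difference | *k* | Expected difference | Power |
|---|---|---|---|
| 60 | 0 | 60 | 98.0% (exact) |
| 60 | 1 | 57 | 97.1% |
| 60 | 2 | 54 | 95.3% |
| 60 | 3 | 51 | 92.8% |
| 60 | 4 | 48 | 88.5% |
| 40 | 0 | 40 | 76.4% (exact) |
| 40 | 1 | 38 | 71.7% |
| 40 | 2 | 36 | 64.2% |
| 0 | 1 | 0 | 3.9% (rejection rate) |

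The simulated mean differences at 60 points were 57.1, 53.9, 51.2 and 48.0 for *k* = 1 to 4, in line with the formula.

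**The case against.** The strongest reply is that Month 12 is reached only by inference. The J2R sentence is written for the primary time point, and Month 12 is to be handled similarly, not identically. The method is called a wash-out, which suggests patients who have stopped drug. The protocol also gives no rule for missed visits in patients who do not discontinue, so own-arm imputation for them is a SAP choice and not protocol text being restored.

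The affected group may also be nearly empty. The SAP 4.2.4 windows for Weeks 51 and 53 together span Days 331 to 379 (49 days), and one value is enough. Local-laboratory results can fill in, failed samples are redrawn, and home visits are allowed. A completer with nothing in that span may well have left the study, in which case the protocol's own J2R applies.

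Finally, the bias is conservative. The results summary bound with the protocol reports that 50 mg was not significant at Month 6, so under the hierarchy the secondary family is exploratory. Tipping-point analyses are planned for the Month 12 lipid endpoints.

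The points on rarity, direction and gatekeeping stand and limit the size of the problem. The point about the protocol's silence also stands: the conflict is with its restriction on J2R. The argument from similarity does not remove the problem. The code includes month12, step 3 names no time point, and no sentence exempts completers. The tipping-point analyses start from the same imputed values, so they can shift those values but do not separate completers from dropouts. The simulation is illustrative: it uses unadjusted normal percent changes, whereas the SAP imputes on the log scale and fits an ANCOVA.

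**Conclusion.** The concern holds. As written, the J2R fallback replaces the own-arm Month 12 value of an active-arm patient who completed dosing and stayed in the study with a placebo prediction. This conflicts with the restriction in Protocol 10.6.3.1 and is not declared in SAP 4.13.

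The effect is likely to be small. It arises only if the fallback is used (the SAP does not define a sufficient number of retrieved dropouts) and only when both Month 12 values are missing. The primary Month 6 comparison is not affected in this way. At a 60-point difference, one or two affected patients cost about 1 to 3 points of power, and power falls below 90% only with four of 20. At 40 points, two affected patients cost about 12 points. Type I error is not inflated. Confirmatory testing is affected only if both doses are significant at Month 6; otherwise only the reported Month 12 estimates are. The number affected is not in the documents, and the protocol expects little missing data.

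**What to change.** In the J2R sentence of SAP 4.9.1.2 and in step 3 of the algorithm, restrict J2R to active-arm patients who discontinued, for values missing after discontinuation. State whether this means discontinuing the study or Study Drug, and reconcile it with Protocol 10.6.3.1. The choice matters because it decides how a patient who leaves between dose 13 and Week 51 is handled. Keep the step 1 own-arm values for all other missing data, including completers who miss both Weeks 51 and 53. Item 2 of Sensitivity Analysis 3 should be aligned in the same way. If the present rule is intended, record it in SAP 4.13 as a change from the protocol.

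The cost is two SAP sentences (a third if item 2 is aligned) and one programming condition on disposition data already collected. No new data are needed.
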